### **1 1. Intervention methods**

The control group received routine rehabilitation training: with the help of rehabilitation therapists, corresponding muscle strength training, comprehensive training of hemiplegic limbs, balance function training, limb neuromuscular electrical stimulation, acupuncture and other comprehensive rehabilitation treatments were carried out according to the patient's functional injury site. On this basis, the observation group added an EDP-D2 external diaphragm pacemaker (Zhongke Tyco (Guangzhou) Electronic Technology Co., Ltd.) for treatment. The specific operation steps are as follows: After

disinfecting the skin, place the small electrode pads on the lower 1/3 of the outer edge of the sternocleidomastoid muscles on the left and right sides, and place the large electrodes on the surface of the pectoralis major muscles on both sides, and fix them with medical tape. The pacing frequency and stimulation intensity are adjusted by the degree of stimulation. Each treatment time is 20 minutes, once a day, 5 days a week, and the treatment course is 4 weeks.

## **12. Measurement indicators**

(1) Pulmonary function measurement: Use an exercise cardiopulmonary testing system (Nanjing Hanya Smax58ce) to test the patient's lung function before treatment and 4 weeks after treatment, including forced vital capacity (FVC), forced expiration in 1 second Forced Expiratory Volume in 1 second (FEV1), FEV1/FVC (%), standing and supine vital capacity (Position vital capacity, VC), and calculate the change percentage of vital capacity from standing to supine position  $[\Delta VC (\%) : (upright vital capacity - supine vital capacity) / supine vital capacity (\%)]$ .

(2) Diaphragm function evaluation: The American Sonosonic portable color ultrasound (M-Turbo) was used to measure the diaphragmatic excursion of quiet breath (DE-QB) on the hemiplegic side of the two groups of patients before treatment and 4 weeks after treatment. and forced breathing diaphragm mobility (Diaphragmatic excursion of deep breath, DE-DB), and measure the thickness of the hemiplegic side diaphragm (The thickening of the diaphragm, Tdi) at the end of expiration and end of inhalation to calculate the diaphragm thickening rate [Thickening fraction, TF: (diaphragm thickness at end-inspiration - diaphragm thickness at end-expiration) / diaphragm thickness at end-expiration (%)].

(3) The Modified Trunk Impairment Scale to Norwegian Version ( mTIS ) is used to evaluate the patient's trunk balance ability before treatment and after 4 weeks of treatment.

## **1 3. Definition of effective identification of test participants**

Effective: The patient's intervention time is 4 weeks, and the patient's treatment is basically completed . The measurement indicators are completed according to standards and the data is complete .

Withdrawal: Due to personal reasons, incompatibility with treatment, dissatisfaction with the research process or other reasons.

Exclusion: Patients with severe comorbidities or complications who do not participate in the study.

Loss to follow-up: The patient was suddenly discharged from hospital or transferred to another department during the trial, resulting in the continuation of the study.

Confounding (confounding): A situation in which external factors or indicators have a false influence on the research results.

Suspension: Refers to the premature termination of a study, which may be due to unpredictable safety issues, poor treatment efficacy, or other serious problems that have to stop the trial.

Suspension: Suspension may occur due to safety issues, concerns about treatment efficacy, or other reasons that require further investigation.

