## **9. Inclusion and exclusion criteria**

Inclusion criteria: ①Patients who meet the diagnostic criteria for stroke for the first time; ②Patients whose disease duration is within 6 months, have received specialist and standardized treatment, and have stable vital signs; ③are informed of this study, voluntarily accept rehabilitation treatment, and sign an informed consent form; ④no chronic breathing before and after stroke History of systemic and circulatory diseases. ⑤ The patient can maintain the starting posture evaluated by the mTIS scale for 10 seconds. The standard for the starting posture is: sitting on the edge of the bed without any support for the back and arms, with the thighs in full contact with the bed surface, and with the feet flat and the same width as the hips. On the ground, bend your knees 90° and place your arms on your thighs.

Exclusion criteria: ① People with severe heart, lung and other organ function diseases, such as pulmonary embolism, pacemaker placement, etc.; ② People with severe cognitive impairment and abnormal hearing and understanding; ③ People who are not suitable for electrical stimulation treatment Other reasons include sudden instability of vital signs, malignant tumors, combined mental illness, etc.

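### Safety is named as a ground for stopping or suspending the trial, but no adverse events are recorded and two exit categories do not ask whether a harm was the cause

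*Protocol*

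**What the plan says.** Protocol section 13 has two entries under the label of suspension. One describes early termination, "which may be due to unpredictable safety issues, poor treatment efficacy, or other serious problems that have to stop the trial". The other describes a pause: "Suspension may occur due to safety issues, concerns about treatment efficacy, or other reasons that require further investigation". Both name safety, and neither gives an event, a reviewer or a time of review.

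The same section sorts individual patients. Withdrawal is "Due to personal reasons, incompatibility with treatment, dissatisfaction with the research process or other reasons". Loss to follow-up is "The patient was suddenly discharged from hospital or transferred to another department during the trial", followed by a clause on the consequence for the study. Exclusion is "Patients with severe comorbidities or complications who do not participate in the study". A patient counts as effective after 4 weeks of intervention with treatment basically completed, and further: "The measurement indicators are completed according to standards and the data is complete".

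Section 12 lists what is measured: lung function, diaphragm ultrasound on the hemiplegic side, and the mTIS, each before treatment and at 4 weeks. The only other text bearing on safety is an exclusion criterion in section 9 for people unsuited to electrical stimulation. It sets up no data collection.

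**The concern.** A provision to stop or pause for safety needs information on safety, and the protocol plans none. Its exit categories do not supply any either, because they record that a patient left without recording whether a harm was the reason.

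Two things are at stake. First, a report that no safety problem was seen could not be told apart from a report in which nobody was asked to write one down. Second, the patients are inpatients within 6 months of a first stroke, so an unexpected move to a different department can follow a deterioration. If such patients are closed as lost, their 4-week values go missing for a reason tied to their health. The comparison at 4 weeks then rests on those who stayed well enough to remain, and any imbalance in such exits between the arms would bias it.

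**Working it through.** No arithmetic applies, since the protocol states no figure on this point. The check sets the sections side by side.

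1. **What could prompt a halt (section 13).** Safety is named in two provisions, early termination and suspension. Neither has a stated criterion.

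2. **What is planned to be collected (section 12).** There are three groups of measures, none of which is a safety measure. They are taken at two time points, before treatment and at 4 weeks, with no assessment planned in between.

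3. **Whether another section fills the gap.** Section 9 screens patients at entry. Section 11 describes the treatments and the session schedule but asks for no record of tolerability or events. Section 14 covers tests and correlations. No section defines, records, reviews or reports adverse events.

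4. **How exits are classed (section 13).** Two categories apply to individual patients already in the trial:
   - Loss to follow-up covers sudden discharge or transfer. No cause is requested.
   - Withdrawal puts treatment incompatibility between personal reasons and dissatisfaction. The wording may mean that the patient could not tolerate treatment or that the patient did not cooperate. The category does not separate the two.

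5. **Tracing a case.** Suppose one patient is moved to a different department between baseline and week 4 because of deterioration, and another is moved for an administrative reason. Under section 13 both can be classed as lost to follow-up. Under section 12 neither has any planned record between the baseline values and the missing 4-week values. The data the plan asks for would be the same for both, so the difference that matters for a safety decision is not captured.

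6. **Effect on the outcome data.** Neither patient meets the definition of an effective participant, which requires complete data. The protocol does not say that only effective participants are analysed, so this step shows lost outcomes and not a stated restriction of the analysis.

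**The case against.** The strongest reply is that an exit category is not an adverse-event code. A patient can be lost to follow-up and also have an event on file, and nothing in section 13 forbids noting a cause. Suspension is worded as something that may happen, so it could rest on what ward staff see. This stands to a point: the supportable statement is that no safety data are planned, not that none could exist. It does not remove the gap, because nothing in the protocol asks for the event or the cause. Nor can an unseen SAP close it, since an SAP cannot analyse what was never collected.

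The loss-to-follow-up line also ends with a clause that reads as garbled and probably means that participation could not continue. On that reading, a transferred patient who can still be assessed is not lost. The clause should say so plainly, and cause remains unasked on either reading.

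A reader might infer more than the text supports:

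- **That on-study complications are misfiled as exclusions.** The line is limited to people who do not take part, which reads most naturally as before entry.
- **That intolerance is filed as withdrawal.** The protocol's word is incompatibility, which is open to both meanings given above.
- **That a patient who becomes unstable under stimulation can be relabelled as excluded.** Section 9 does list "Other reasons include sudden instability of vital signs, malignant tumors, combined mental illness", but among entry criteria, and no sentence allows a randomised patient to be reclassified.
- **That these exits are probably harms.** Transfer, discharge and withdrawal can all be unrelated to harm. They are possible harms.
- **That a safety trigger has been disabled.** No trigger is stated; there are two definitions that mention safety.

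**Conclusion.** The point holds as an omission with a practical consequence. Safety is a named ground for termination and suspension, no planned measure informs it, and the two on-study exit categories do not ask whether a harm was the cause. Possible harms can leave unrecorded, and 4-week outcomes can be lost for health-related reasons.

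Its size cannot be given as a rate or a bias. The protocol states 30 patients for the first phase but no split between the arms, no total for the continued recruitment and no expected frequency of events or transfers. The conclusion assumes only that some transfers, discharges or withdrawals may be health-related, and that no separate adverse-event procedure exists outside the protocol shown. It does not by itself invalidate the planned efficacy comparison. It is a change that should be made because it is cheap and the missing information cannot be recovered reliably later.

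**What to change.** In section 12, add adverse events through week 4 in both arms, recorded at existing treatment contacts, and state that this record is available to whoever decides on suspension. Section 11 gives a session schedule for the pacing treatment but no contact frequency for routine rehabilitation, so the protocol should set the same frequency of asking in both arms. Otherwise events would be sought more often in the pacing arm.

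In section 13:

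- Record the reason for every transfer, discharge and withdrawal, and separate harm-related from personal reasons.
- Limit loss to follow-up to patients who cannot be assessed, and correct the closing clause of that line.
- Still attempt the 4-week assessment in patients who were transferred or discharged.
- State that exclusion applies only before randomisation.

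The cost is protocol wording, slightly more data entry, and some effort to reach and assess patients who have moved department or gone home. No treatment or clinical rule changes. Section 6 has recruitment continuing to 30 September 2024, so patients in the second stage could be covered.

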#### **14. Statistical analysis methods**

All data were analyzed using spss26.0, count data were expressed as frequencies, and Fisher's exact probability method was used; for measurement data that conformed to normal distribution, the independent sample t test was used for comparison between groups, and Pearson correlation analysis was used for correlation; if it did not conform to normality Rank sum test was used for comparison of distribution between groups, and Spearman correlation analysis was used for correlation.  $P<0.05$  was considered as a statistically significant difference.

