#### 4. Research purpose

Apply EDP to treat stroke patients, observe the improvement of trunk balance ability, lung function and diaphragm function in stroke patients, and analyze the correlation between trunk balance ability and respiratory function indicators.

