#### 5. Design plan

#### 6. Research matters execution process

2023.01.01 to 2023.08.01 , and relevant data before and after the intervention will be entered and sorted. Continue to review relevant domestic and foreign literature related to this topic and make a summary.

2023.08.02-2023.09.30 The first stage of data analysis, discussion of results, and writing of the paper.

2023.09. 3 0-2024.09.30 Continue to recruit subjects , conduct second-stage data analysis, discuss results, and write papers .

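### Section 14 tests between groups without the baseline values the trial collects: valid, but less precise unless the baseline to week-4 correlation is very low or very high

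*Protocol*

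**What the plan says.** Every measurement outcome in Protocol section 12 is taken twice. The plan is to "test the patient's lung function before treatment and 4 weeks after treatment". Diaphragm ultrasound is done "on the hemiplegic side of the two groups of patients before treatment and 4 weeks after treatment". The mTIS is used to assess "trunk balance ability before treatment and after 4 weeks of treatment". Section 4 gives the aim as to "observe the improvement of trunk balance ability, lung function and diaphragm function in stroke patients", and section 6 says that "relevant data before and after the intervention will be entered and sorted".

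Section 14 is the only analysis method stated, although section 6 plans two stages of analysis. For normally distributed measurement data "the independent sample t test was used for comparison between groups"; "if it did not conform to normality Rank sum test was used for comparison of distribution between groups". No baseline covariate is named.

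**The concern.** The baseline of each outcome will be in the data set, but neither named test adjusts for it. A baseline that predicts the 4-week value explains part of the variation between patients, and a model that includes it estimates the group difference more precisely at no cost in data. The first phase has only 30 patients (section 7), so precision is scarce. The proportion of variance saved hardly changes with sample size, so the point also applies to the second stage.

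The two possible readings of section 14 fail in opposite places. A test on week-4 values wastes most when r is high, and a test on changes wastes most when r is low. Adjustment avoids having to guess r.

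**Working it through.** **The plan's own figure.** The only figure is 30 first-phase patients, given without effect size, SD or power, so there is nothing to reproduce.

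**Inputs.** From the protocol: 30 first-phase patients (section 7), two randomised groups (section 10), significance at P<0.05 (section 14). Assumed: equal arms (n = 15 each), two-sided testing, equal SDs at both times, r over a range, true effects of 0.5 or 0.8 SD. The second-stage total is not stated, so 30 per arm is only an illustration.

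**Variance of the estimated difference (SD = 1).**
- t test on week-4 values: 2/n
- t test on changes: 2(1−r) × 2/n
- Baseline-adjusted model: (1−r²) × f × 2/n, where f = 1 + 1/(2n−4) is the cost of estimating the slope. At n = 15, f = 1 + 1/26 = 1.0385; at n = 30, f = 1 + 1/56 = 1.0179.

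**Variance saved at n = 15.**
- Against week-4 values, 1 − (1−r²)f: r = 0.5 gives 1 − 0.75 × 1.0385 = 22%; r = 0.7 gives 1 − 0.51 × 1.0385 = 47%.
- Against changes, 1 − ((1+r)/2)f: r = 0.5 gives 1 − 0.75 × 1.0385 = 22%; r = 0.7 gives 1 − 0.85 × 1.0385 = 12%.

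At n = 30 the four figures are 24%, 48%, 24% and 14%.

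**Where the gain ends (n = 15).** Against week-4 values, (1−r²)f = 1 gives r = √(1/27) = 0.19. Against changes, ((1+r)/2)f = 1 gives r = 2/1.0385 − 1 = 0.93.

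**Power, normal data** (noncentral t; the adjusted model has one degree of freedom fewer):

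| Setting | Test | r=0 | 0.3 | 0.5 | 0.7 | 0.8 |
|---|---|---|---|---|---|---|
| 15 per arm, 0.8 SD | Week-4 | 56.2% | 56.2% | 56.2% | 56.2% | 56.2% |
| | Change | 32.2% | 43.2% | 56.2% | 77.9% | 91.7% |
| | Adjusted | 54.6% | 58.5% | 66.8% | 82.7% | 93.2% |
| 30 per arm, 0.5 SD | Week-4 | 47.8% | 47.8% | 47.8% | 47.8% | 47.8% |
| | Change | 27.0% | 36.3% | 47.8% | 69.1% | 85.3% |
| | Adjusted | 47.1% | 50.7% | 58.7% | 75.3% | 88.2% |

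The largest loss in the table is 56.2 − 54.6 = 1.6 points, at r = 0.

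**Validity.** In 40,000 simulated null trials at 15 per arm (r = 0.5 and 0.8), type I error was 5.0% and 5.1% for the week-4 t test, 5.0% and 4.9% for the change t test, and 4.5% and 4.6% for the rank-sum test on week-4 values.

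**Chance imbalance.** A baseline difference D moves the week-4 estimate by rD and the change estimate by (1−r)D the other way. Its SD is √(2/15) = 0.365, so it exceeds 0.5 SD in 17% of randomisations per outcome. Given a difference of exactly 0.5 SD and no true effect, error at r = 0.5/0.7/0.8 is 7.0/8.0/7.8% for week-4 values, 7.1/6.4/5.8% for changes and 4.9–5.0% after adjustment.

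**Skewed errors** (lognormal, sigma 0.8). These simulations compare section 14's rule, with a Shapiro-Wilk switch at 0.05 on raw values or changes, with an adjusted rule that takes its P value from ranked baseline and 4-week values when the residuals fail the same test.
- 15 per arm, 0.8 SD, r = 0/0.3/0.5/0.7/0.8: section 14 on week-4 values 88/84/79/78/78%; on changes 50/66/78/93/98%; adjusted rule 88/87/88/92/95%.
- 15 per arm, 0.5 SD, r = 0.8: changes 81.7% against adjusted 74.4%, or 80.6% against 70.4% with a normal baseline. A separate run of the first setting gave 80.9% against 75.0%.
- 15 per arm, 0.5 SD, r = 0.9: 96.7% against 88.0%.
- 30 per arm, 0.5 SD, r = 0.8: 98.8% against 95.5%.

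**The case against.** The strongest reply is that nothing here is an error. Section 14 contradicts no other section, its tests hold their level, and a statistical analysis plan that is not shown could add covariates. Part of this stands: the silence on whether week-4 values or changes are compared can be left to such a plan and is no fault in itself. But the protocol does name the between-group test, and the named test leaves out the baseline.

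The size is also open to challenge, because r, the effect, the arm ratio and the second-stage total are all absent. Section 4 speaks of improvement, which makes a test on changes plausible, and against changes the benefit shrinks as r rises. With strongly skewed errors and high r, adjustment loses power. All of this stands and bounds the claim.

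Three stronger readings are tempting:
- **That the unadjusted tests are biased or invalid.** Section 10 states random allocation, and the simulated error rates are at or just below 5%.
- **That the conditional error of up to 8% is a second fault.** It is the same lost precision viewed after fixing a particular imbalance; averaged over randomisations the error is 5%.
- **That precision is lost whatever r is.** The limits at about 0.19 and 0.93 rule that out.

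**Conclusion.** The point holds as a conditional loss of precision and justifies a change that should be made, with medium confidence. Section 14 fixes valid tests that ignore a baseline already collected. With normal data, r = 0.5, 15 per arm and an effect of 0.8 SD, either unadjusted test has 56% power and the adjusted model 67%. Away from r = 0.5 the gain depends on which unadjusted test would have been used. These sizes rest on equal arms, equal SDs at both times, two-sided testing and assumed values of r and effect. Validity here means each test taken singly; repeated testing across the two stages is a separate matter.

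**What to change.** In section 14, replace the between-group t test for each measurement outcome with: a linear model of the 4-week value on group plus that outcome's own baseline value, reporting the adjusted between-group difference with its 95% CI. Judge normality on the model residuals. Where they are clearly non-normal, report a baseline-adjusted rank analysis (the same model on the ranks of the baseline and 4-week values) beside the model result, and state in advance which P value decides. A bootstrap interval is not needed: with skewed errors at 15 per arm the model interval covered about 96%.

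Apply this at the second stage. Section 6 schedules "2023.08.02-2023.09.30 The first stage of data analysis, discussion of results, and writing of the paper"; if that analysis has been done, label the adjusted first-stage result post hoc. If those patients are pooled into the second stage, state that the model was chosen after their data were analysed.

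Cost: no new data, visits or patients; one degree of freedom; under 2 points of power if r is near zero. With strongly skewed errors and high r, it costs roughly 3 to 10 points against a rank-sum test on changes: about 7–10 at 15 per arm, 0.5 SD and r = 0.8, about 9 at r = 0.9, and about 3 at 30 per arm and r = 0.8. These costs were computed with the rank analysis supplying the P value when residuals are non-normal, and do not carry over if the model's P value decides.

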#### 7. Recruitment of participants

30 stroke patients admitted to the Department of Rehabilitation Medicine of the First Affiliated Hospital of Anhui Medical University from January 2023 to August 2023 were randomly selected in the first phase .

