## **10. Grouping method**

Eligible patients were recruited by members of the project team and divided into experimental groups and control groups through a random number table method . Subjects were randomly enrolled and were unaware of their grouping , and only some researchers were informed of the grouping .

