#### **15. Expected results**

EDP therapy contributes to the restoration of respiratory function and trunk balance in stroke patients. Additionally, the trunk balance ability in stroke patients displays a correlation with Respiratory function.

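### Section 14 names only an unadjusted Pearson or Spearman coefficient for the trunk–respiratory correlation and fixes neither time point nor arm handling; if post-treatment data are pooled across arms, arm would confound it.

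*Protocol*

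**What the plan says.** Section 4 makes the correlation part of the trial's purpose: to "analyze the correlation between trunk balance ability and respiratory function indicators". Section 15 lists it as an expected conclusion, that "the trunk balance ability in stroke patients displays a correlation with Respiratory function", and does not tie it to an arm or a time point. The same section also expects that "EDP therapy contributes to the restoration of respiratory function and trunk balance in stroke patients".

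Section 14 gives the whole stated method for the correlation. If data are normal, "Pearson correlation analysis was used for correlation"; if not, "Spearman correlation analysis was used for correlation". P<0.05 "was considered as a statistically significant difference".

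The design is two-arm: section 10 has patients "divided into experimental groups and control groups through a random number table method", and section 11 adds EDP to routine rehabilitation in one arm only. Under section 12, the modified Trunk Impairment Scale (mTIS), lung function and diaphragm ultrasound are all measured before treatment and at 4 weeks. Nothing says which of these values enter the correlation, or whether the arms are combined. Section 13 defines confounding in general terms, but section 14 does not apply it to this analysis.

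**The concern.** A plain Pearson or Spearman coefficient has no place for a treatment term. In a randomised trial where treatment is expected to shift both variables, arm is a common cause of both. If 4-week or change values from the two arms are put into one coefficient, EDP patients tend to be better on both measures and controls worse on both. The coefficient then mixes the treatment effect with the association between patients that the trial wants to describe.

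The correlation is one of the two conclusions listed in section 15. If it came from the arm difference, it would restate the treatment effect and say nothing new about how trunk control and breathing relate in stroke patients. Switching to Spearman does not help, because ranks carry the same arm shift.

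**Working it through.** The protocol states no effect size, SD, power or sample-size calculation, so there is no figure of its own to reproduce. The check asks how large a correlation arm alone can produce.

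**Inputs from the protocol**
- Unadjusted Pearson or Spearman, threshold 0.05 (section 14).
- Two randomised arms (section 10).
- First phase: "30 stroke patients admitted to the Department of Rehabilitation Medicine" (section 7). Section 6 continues recruitment into a second stage but gives no number.
- Benefit expected on both measures (section 15).

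**Assumptions**
- 1:1 allocation, a two-sided test and normal data.
- Within-arm correlation ρ = 0.
- The same effect d, in within-arm SDs, on both measures, varied from 0 to 2.
- A total of 60 is shown only as an illustration of a larger trial.

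**Step 1: induced correlation.** Pooling two equal arms adds d₁²/4 and d₂²/4 to the two unit variances and d₁d₂/4 to the covariance:

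r = (ρ + d₁d₂/4) / √[(1 + d₁²/4)(1 + d₂²/4)]

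With ρ = 0 and d₁ = d₂ = d, this is r = (d²/4)/(1 + d²/4):
- d = 0.5: 0.0625/1.0625 = 0.06
- d = 0.8: 0.16/1.16 = 0.14
- d = 1.0: 0.25/1.25 = 0.20
- d = 1.5: 0.5625/1.5625 = 0.36
- d = 2.0: 1/2 = 0.50

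**Step 2: chance of P<0.05 when there is no correlation within arms.** At n = 30 the critical |r| is 2.048/√(28 + 2.048²) = 0.361. Simulation with 20,000 trials per setting gave:

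| d on both | Pooled Pearson, n=30 | Pooled Spearman, n=30 | Arm-adjusted Pearson, n=30 | Pooled Pearson, n=60 (assumed) |
|---|---|---|---|---|
| 0 | 5.0% | 5.0% | 5.0% | 4.8% |
| 0.5 | 6.2% | 6.1% | 5.1% | 7.6% |
| 0.8 | 11.5% | 11.8% | 5.1% | 17.8% |
| 1.0 | 18.8% | 19.1% | 4.7% | 34.5% |
| 1.5 | 54.2% | 57.2% | 5.1% | 85.1% |
| 2.0 | 88.5% | 91.0% | 4.9% | 99.6% |

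**Step 3: where the problem disappears.** If EDP moves one measure by d = 1 and the other not at all, the n = 30 rate is 5.1%. The d = 0 row is the pre-treatment case, since EDP cannot yet have acted: 5.0%. Adjusting for arm gives 4.7% to 5.3% at every d from 0 to 2 and at n of 30, 60 and 100.

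**Step 4: which d is relevant.** With 15 per arm, the normal approximation to the power of a group comparison at d = 1.02 is Φ(1.02 × √7.5 − 1.96) = Φ(0.83), about 80%. An effect that 30 patients would detect reliably is therefore near d = 1, where the induced r is 0.20 and the false-positive rate about 19%.

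**The case against.** A reader might infer that the plan commits to pooling the arms after treatment, so that an EDP effect would itself manufacture the reported correlation. The documents do not support this. Section 14 does not say that arms are combined or that 4-week or change values are used. A harmless reading is open: section 3 describes the question as an unresolved association in stroke patients, section 15 claims it for stroke patients generally, and section 12 provides pre-treatment values for everyone. On pre-treatment values, or within each arm, there is no such bias. Section 4, however, mentions the correlation alongside improvement under EDP, so the text does not settle the time point either way.

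It can also be said that time point, analysis set and covariates usually belong in a statistical analysis plan, which may exist. That stands for the silence taken alone. It does not fully answer the point, because section 14 does choose a method, and neither coefficient it names can carry an arm term. A plan that adjusted for arm would have to add to or replace what is written.

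The size is also open to challenge. At d = 0.5 the distortion is slight, and an effect on only one measure produces none. Even at d = 1 and n = 30, roughly four in five analyses would not reach significance. Large inflation needs d near 1.5 on both measures, or a larger total than the protocol states. All of this stands. Nor do the documents show that the true within-arm correlation is zero; that assumption isolates the part due to arm and does not predict that the trial's finding will be false.

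**Conclusion.** The concern holds in conditional form. Section 14 specifies the correlation only as an unadjusted coefficient and leaves time point and arm handling open. One permitted use, pooling 4-week or change values across arms, is confounded by arm if EDP improves both measures as section 15 expects.

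At the first-phase size of 30, the false-positive rate ranges from close to nominal at d = 0.5 to just over half at d = 1.5. It is nearly four times nominal around d = 1, the size of effect that such a trial can reliably detect. These figures rest on the assumptions listed in the working; the protocol supplies neither d nor a total sample size. The point is worth correcting because it bears on one of the two expected conclusions and costs almost nothing to close. It is not evidence that the planned correlation is wrong.

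**What to change.** In section 14, state that the correlation between mTIS and each respiratory index is based on pre-treatment values of all randomised patients, with Pearson or Spearman chosen as now. Add that any correlation of 4-week or change values will be reported only as a partial (or rank-based partial) correlation adjusted for arm, or as separate within-arm coefficients.

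This takes about two sentences and no new data. Arm adjustment costs one degree of freedom (27 instead of 28 at n = 30). Within-arm coefficients cost more precision: with an assumed 15 per arm, the critical |r| rises from 0.361 to 2.160/√(13 + 2.160²) = 0.514. The two analyses answer different questions: the pre-treatment one asks whether the functions are related in these patients, and the adjusted change analysis asks whether they improve together beyond what arm explains. The text should say which one supports the conclusion in section 15.
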